15.5. Study and Study Center Closure

Upon completion of the study, the monitor will conduct the following activities in conjunction with the investigator or study center personnel, as appropriate:

- Return/provide all study data to the sponsor
- Resolution and closure of all data queries
- Accountability, reconciliation, and arrangements for unused study drug(s)
- Review of study records for completeness
- Collection of all study documents for the trial master file filing according to GCP and local regulation
- Shipment of samples (including but not limited to those for PK, ADA, and biomarkers) to the assay laboratory for central laboratory analysis according to protocol and laboratory manual requirements

In addition, the sponsor reserves the right to suspend the enrollment or prematurely discontinue this study either at a single study center or at all study centers at any time for any reason. Potential reasons for suspension or discontinuation include, but are not limited to, safety or ethical issues or noncompliance with this protocol, GCP, the sponsor's written instructions, the clinical study agreement, or applicable laws and regulations. If the sponsor determines such action is needed, the sponsor will discuss this with the investigator (including the reasons for taking such action) at that time. When feasible, the sponsor will provide advance notification to the investigator of the impending action before it takes effect.

The sponsor will promptly inform all other investigators and/or institutions conducting the study if the study is suspended or terminated for safety reasons. The sponsor will also inform the regulatory authorities of the suspension or termination of the study and the reason(s) for the action. If required by applicable regulations, the investigator must inform the IEC/IRB promptly and provide the reason for the suspension or termination.

If the study is prematurely discontinued, all study data must still be provided to the sponsor. In addition, arrangements will be made for the return of all unused study drug(s) in accordance with the applicable sponsor procedures for the study.

Financial compensation to the investigators and/or institutions will be in accordance with the clinical study agreement established between the investigator and/or institutions and the sponsor.

15.6. Information Disclosure and Inventions

All rights, title, and interests in any inventions, know-how, or other intellectual or industrial property rights that are conceived or reduced to practice by the study center personnel during the course of or as a result of the study are the sole property of the sponsor and are hereby assigned to the sponsor.

If a written contract for the conduct of the study, which includes ownership provisions inconsistent with this statement, is executed between the sponsor and the study center, that contract's ownership provisions shall apply rather than this statement.

All information provided by the sponsor and all data and information generated by the study center as part of the study (other than a subject's medical records) are the sole property of the sponsor and will be kept confidential by the investigator and other study center personnel.

This information and data will not be used by the investigator or other study center personnel for any purpose other than conducting the study without the prior written consent of the sponsor.

These restrictions do not apply to:

- Information that becomes publicly available through no fault of the investigator or study center personnel
- Information that is necessary to disclose in confidence to an IEC/IRB solely for the evaluation of the study
- Information that is necessary to disclose to provide appropriate medical care to a subject
- Study results that may be published as described in Section [15.4](#).

If a written contract for the conduct of the study, which includes provisions inconsistent with this statement is executed, that contract's provisions shall apply rather than this statement.

APPENDIX 1. SCHEDULE OF ASSESSMENTS

Period	Screening	Admission to Unit	Treatment	Follow-up													
Day	-28 to -1	-1	D1 ^a	D2	D3	D4	D5	D8	D15	D22	D29	D43	D57	D71	D85	D113 / EOS ^b	Safety Follow-up Visit ^c
Visit Window (day)	--	--	--	--	--	--	--	--	± 1	± 1	± 1	± 2	± 2	± 2	± 2	± 2	± 3
Informed consent ^d	X																
Inclusion/exclusion criteria ^e	X	X															
Demography/prior medications	X																
Medical history	X																
Randomization ^f		X															
BGB-DXP604 single dose administration ^g			X														
BGB-DXP593 single dose administration ^g			X (Part 2 only)														
Discharge					X												
Safety Assessments																	
Vital signs/ height and weight ^h	X	X	X	X	X	X	X	X	X	X	X	X	X	X	X	X	X
Complete physical examination ⁱ	X																

Period	Screening	Admission to Unit	Treatment	Follow-up														
				D2	D3	D4	D5	D8	D15	D22	D29	D43	D57	D71	D85	D113 / EOS ^b	Safety Follow-up Visit ^c	
Day	-28 to -1	-1	D1 ^a															
Visit Window (day)	--	--	--	--	--	--	--	--	--	± 1	± 1	± 1	± 2	± 2	± 2	± 2	± 2	± 3
Targeted physical examination ⁱ			X	X	X	X	X	X	X	X	X	X	X	X	X	X	X	X
12-lead ECG ^j	X		X	X	X	X	X	X	X	X	X	X	X	X	X	X	X	X
Cardiac Telemetry ^k			X	X														
Prior/Concomitant medications review	X																	
Adverse event review ^l	X																	
Laboratory Assessments																		
Hematology ^m	X	X		X	X		X	X	X	X		X		X	X	X	X	
Clinical chemistry ^m	X	X		X	X		X	X	X	X		X		X	X	X	X	
Coagulation ^m	X	X		X	X		X	X	X	X		X		X	X	X	X	
IgG to SARS-CoV-2	X																	
rRT-PCR test for COVID-19 (nasopharyngeal or oropharyngeal swab)	X											X						
Urinalysis ⁿ	X	X		X	X		X	X	X	X		X		X	X	X	X	
Alcohol/drugs screen ^o	X	X																
PK and ADA blood sampling			See Appendix 2 and Appendix 3															
Hepatitis B and C testing	X																	

Period	Screening	Admission to Unit	Treatment	Follow-up														
				D2	D3	D4	D5	D8	D15	D22	D29	D43	D57	D71	D85	D113 / EOS ^b	Safety Follow-up Visit ^c	
Day	-28 to -1	-1	D1 ^a															
Visit Window (day)	--	--	--	--	--	--	--	--	--	± 1	± 1	± 1	± 2	± 2	± 2	± 2	± 2	± 3
Pregnancy test (if applicable) ^p	X	X									X		X		X	X		
HIV test	X																	

Abbreviations: ADA, antidrug antibody; AEs, adverse events; COVID-19, Coronavirus Disease 2019; D, day; ECG, electrocardiogram; EOS, End-of-Study; HIV, human immunodeficiency virus; Ig, immunoglobulin; IRT, Interactive Response Technology; PK, pharmacokinetic; rRT-PCR, real-time reverse transcription-polymerase chain reaction; SAEs, serious adverse events; SARS-CoV-2, severe acute respiratory syndrome coronavirus 2.

- ^a The schedule of assessments for Day 1 under different timepoints are provided in [Appendix 2](#).
- ^b The EOS Visit will be conducted within 7 days after a premature study discontinuation. The Day 113 Visit is the EOS Visit for subjects who complete all previously planned study visits.
- ^c The Safety Follow-up Visit is only for subjects who discontinue the study within 30 days after the dose of study drug. The Safety Follow-up Visit will be conducted on 30 days after the dose of the study drug (± 3 days). If the premature discontinuation from study occurs within 7 days before the timepoint of 30 days after the dose of the study drug, the Safety Follow-up Visit could be combined with the EOS Visit as appropriate.
- ^d The informed consent must be obtained before performing any study-specific procedures. Consent must be obtained using the current version of the form approved by the Independent Ethics Committee/Institutional Review Board.
- ^e Follicle-stimulating hormone and estradiol assessments will be performed on female subjects who are < 55 years of age with no spontaneous menses for ≥ 12 months to identify the status of no childbearing potential. Female subjects of no childbearing potential and female subjects of childbearing potential who are willing to use a highly effective method of birth control are eligible to participate.
- ^f Subjects will be randomized into either the active arm or control arm via IRT. Randomization will occur after the admission on Day -1 and before the dose of study drug on Day 1.
- ^g The dose will be based on the subject's actual body weight 1 day before the administration of study drug(s) (Day -1). In Cohort 2A, BGB-DXP593 should be administered first and BGB-DXP604 should be administered ≥ 30 minutes after the completion of BGB-DXP593 infusion.
- ^h Height and weight will be measured at screening, and weight will be measured again on Day -1.
- ⁱ Complete physical examination includes evaluations of 1) head, eyes, ears, nose, and throat; 2) cardiovascular; 3) dermatological; 4) musculoskeletal; 5) respiratory; 6) gastrointestinal; and 7) neurological systems. At subsequent visits (and as clinically indicated), limited, symptom-directed physical examinations will be performed.
- ^j At each timepoint, 3 consecutive 12-lead ECGs will be performed approximately 2 minutes apart and within a maximum of 10 minutes to calculate heart rate and measure QT and QTcF intervals.
- ^k The cardiac telemetry will be performed from approximately 1 hour predose to 24 hours post dosing.

- ^l After informed consent has been signed but before administration of the study drug, only SAEs should be reported. After initiation of the study drug, all AEs and SAEs, regardless of relationship to study drug, will be reported until 30 days after the dose of study drug or EOS Visit, whichever is later. After the period, the investigator should report any SAEs that are considered to be related to the study drug.
- ^m Hematology, clinical chemistry, and coagulation will be evaluated by a local laboratory. The list of hematology, clinical chemistry, and coagulation parameters is provided in [Appendix 4](#).
- ⁿ Collect sample for urine analysis as well as urine microscopy. The urine microscopy will be performed if the urinalysis parameter, such as leukocyte, is out of normal range.
- ^o During the screening, a urine sample will be collected for the screening of drugs; a breath test will be performed for the screening of alcohol.
- ^p Pregnancy test will be performed for female subjects of childbearing potential during the study. The urine pregnancy test will be performed at the Screening Visit, and the next urine pregnancy test will be conducted after the admission on Day -1 and before the dose of study drug on Day 1. Female subjects of childbearing potential with negative results will be eligible to receive the study drug. Afterwards, urine pregnancy test will be performed. A serum pregnancy test must be performed if the urine pregnancy test is positive or equivocal.

APPENDIX 2. SCHEDULE OF ASSESSMENT FOR DAY 1

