4.1. Inclusion Criteria

Each subject must meet all the following inclusion criteria to be considered eligible for participation in this study:

1. Male and female subjects 18 to 60 years of age, inclusive, at the time of signing the informed consent
2. Subjects are in good general health as determined by the investigator or medically qualified designee, based on a medical evaluation including medical history, physical examination, laboratory tests, and cardiac monitoring
3. Body weight ≥ 50 kg and body mass index (BMI) within the range 18 to 32 kg/m² (inclusive)

Note: BMI = weight [kg] / (height [m])²

4. Negative SARS-CoV-2 serology test
5. Negative for COVID-19 based on the nasopharyngeal or oropharyngeal swab with the method of real-time reverse transcription-polymerase chain reaction (rRT-PCR)
6. Female subjects of childbearing potential must be willing to use a highly effective method of birth control (see [Appendix 5](#)) from the time of study enrollment until 4 months after the single dose of study drug(s)
7. Male subjects with female partners of childbearing potential must be willing to use a highly effective method of birth control (see [Appendix 5](#)) from the time of study enrollment until 4 months after the single dose of study drug(s)
8. Able to provide written informed consent and can understand and agree to comply with the requirements of the study and the schedule of assessments.

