4.2. Exclusion Criteria

Subjects who meet any of the following criteria will be excluded from this study.

Medical Histories or Conditions

1. History or presence of cardiovascular, respiratory, hepatic, renal, gastrointestinal, endocrinological, hematological, or neurological disorders capable of significantly altering the absorption, metabolism, or elimination of drugs, constituting a risk to the subject when receiving the study drug; or interfering with the interpretation of data
2. Systolic blood pressure > 150 mmHg at screening
3. Any malignancy within the past 5 years except for basal cell or squamous carcinomas of the skin that has been resected with no evidence of metastatic disease for 3 years

4. Any history of a severe allergic reaction before enrollment that has a reasonable risk of recurrence during the study
5. A medical history of SARS infection
6. Any acute fever disease or infections
7. Any chronic or clinically significant medical condition that, in the opinion of the investigator, would jeopardize the safety or rights of the subject, including but not limited to type 1 diabetes mellitus, chronic hepatitis; or clinically significant forms of: drug or alcohol abuse, asthma (except for childhood asthma), autoimmune disease, psychiatric disorders, or heart disease
8. Platelet disorder or other bleeding disorder may cause injection contraindication
9. Alanine aminotransferase and/or aspartate aminotransferase > 1.5 x upper limit of normal (ULN)
10. Bilirubin > 1.5 x ULN (isolated bilirubin > 1.5 x ULN is acceptable if bilirubin is fractionated and direct bilirubin < 35%)
11. Current or chronic history of liver disease or known hepatic or biliary abnormalities (with the exception of Gilbert's syndrome or asymptomatic gallstones)
12. Average Fridericia's formula (QTcF) > 450 ms (based on triplicate ECGs)
 - NOTE A: The QTc is the QT interval corrected for heart rate according to QTcF, and/or another method. It is either machine-read or manually over-read.
 - NOTE B: The specific formula used to determine eligibility or discontinuation for an individual participant should be determined before initiation of the study. In other words, several different formulas cannot be used to calculate the QTc for an individual participant and then the lowest QTc value used to include or discontinue that participant.

Prior/Concomitant Therapy

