13. Previous receipt of a licensed or investigational biologic agent (such as monoclonal antibodies) within 3 months or 5 half-lives (whichever is longer) before the randomization
14. Previous receipt of a licensed or investigational nonbiologic agent (such as those derived from chemical synthesis) within 1 month or 5 half-lives (whichever is longer) before the randomization
15. Past or intended use of over-the-counter or prescription medication, including herbal medications, within 28 days before the randomization. Use of paracetamol, ibuprofen, and/or vitamins at the recommended dose will be allowed at the investigator's discretion within 28 days before the randomization.

Prior/Concurrent Clinical Study Experience

16. Participation in ≥ 4 clinical studies within 12 months before the randomization
17. Previous participation in Study BGB-DXP593-101.

Diagnostic Assessments

18. Positive HIV antibody test
19. Presence of hepatitis B surface antigen (HBsAg) and/or hepatitis B core antibody (HBcAb) at screening or within 3 months before the randomization
20. Positive hepatitis C antibody test result at screening or within 3 months before randomization

NOTE: Participants with positive hepatitis C antibody due to prior resolved disease can be enrolled if a confirmatory negative hepatitis C RNA test is obtained.
21. Positive hepatitis C RNA test result at screening or within 3 months before randomization

NOTE: Test is optional and participants with negative hepatitis C antibody test are not required to also undergo hepatitis C RNA testing
22. Positive pre-study alcohol/drugs screen.

Other Exclusions

23. Immediate family history of seizures, epilepsy, brain or mental disease at the investigator's discretion
24. The total volume of blood loss > 500 mL within 3 months before randomization
25. Sensitivity to any of the study drug or components thereof, or other allergy that, in the opinion of the investigator or medical monitor, contraindicates participation in the study
26. Anyone who smokes \geq 15 cigarettes per day.

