7.2. Enrollment

7.2.1. Confirmation of Eligibility

The investigator will assess and confirm the eligibility of each subject. All screening results and relevant medical history must be available before eligibility can be determined. All inclusion criteria must be met and none of the exclusion criteria may apply. No eligibility waivers will be granted.

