8.1.1. Demographic Data, Medical History, and Prior Medications

Demographic data will include age or year of birth, gender, and race/ethnicity.

Medical history includes any history of clinically significant disease, surgery history, reproductive status (ie, no childbearing potential or childbearing potential), and smoking history.

Prior medications include all medications (eg, prescription drugs, over-the-counter drugs, herbal medications) used by the subject within 28 days before administration of study drug(s).

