8.2.3. Laboratory Safety Tests

Samples for protocol-specified clinical chemistry, hematology, urinalysis, and coagulation profiles will be evaluated by a local laboratory.

A pregnancy test will be performed for female subjects of childbearing potential during the study. Samples for pregnancy testing will also be assessed locally. The urine pregnancy test will be performed at the Screening Visit, and the next urine pregnancy test will be conducted after the admission on Day -1 and before administration of study drug(s) on Day 1. Female subjects of childbearing potential with negative results will be eligible to receive the study drug(s). Afterwards, urine pregnancy test will be performed. A serum pregnancy test must be performed if the urine pregnancy test is positive or equivocal.

See [Appendix 4](#) for the list of clinical laboratory tests to be performed and [Appendix 1](#) for the timing and frequency. Additional tests may be performed at any time during the study as deemed necessary by the investigator or as required by local regulations. If required by local regulations, clinical laboratory evaluations performed by a local (instead of a central) laboratory are acceptable.

A detailed description of the procedures for sample collection, handling, storage, and shipment of the laboratory samples and all materials such as test tubes and labels are provided in the Laboratory Manual.

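### No eligibility criterion addresses breastfeeding, so a nursing woman who meets the other criteria could receive BGB-DXP604, a first-in-human antibody

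*Protocol*

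**What the plan says.** Three places in the protocol settle which women may be dosed.

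- Inclusion 6 (Section 4.1): "Female subjects of childbearing potential must be willing to use a highly effective method of birth control", from enrolment until 4 months after the single dose.
- Appendix 1, footnote e: women of no childbearing potential qualify, and "female subjects of childbearing potential who are willing to use a highly effective method of birth control are eligible to participate".
- Appendix 1, footnote p, with the same rule in Section 8.2.3: "Female subjects of childbearing potential with negative results will be eligible to receive the study drug". The urine test is done at screening and again between admission on Day -1 and dosing on Day 1. A serum test follows a positive or equivocal urine result.

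Section 7.2.1 decides eligibility on the listed criteria: "All inclusion criteria must be met and none of the exclusion criteria may apply". No waivers are granted. Section 8.1.1 records reproductive status in two categories only, with or without childbearing potential. Section 9.7.5 follows pregnancies in partners of male subjects, pregnancy complications and birth defects. It says nothing about a child who is already being nursed.

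**The concern.** The contraception period and the repeat pregnancy tests during follow-up show that the plan treats prolonged maternal exposure as relevant to offspring. A nursing infant is also offspring, yet no criterion, screening question or instruction deals with one. Such an infant would be a third party who has not consented and stands to gain nothing. Because lactation status is not collected and adverse events are collected for subjects only, the study would not show whether an infant had been exposed or harmed. Section 1.5 itself says that the side effects of BGB-DXP604 in humans are unknown.

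**Working it through.** **1. Is the omission real?** Inclusions 1 to 8 and exclusions 1 to 26 are present with unbroken numbering, so this is not a gap in the text. None names breastfeeding or lactation. Nor do Sections 6.2, 7.3, 8.1.1, 8.2.3, 9.3.1 or 9.7.5, Appendix 1 footnotes e and p, Appendices 4 and 5, or the SAP.

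**2. Would another criterion catch her?** Take a healthy nursing woman with an intrauterine device, which Appendix 5 lists as a highly effective method, and a negative pregnancy test.

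- Inclusion 2 asks for good general health. She has it.
- Inclusion 6 asks for contraception. She uses it.
- Exclusion 1 concerns disorders that alter drug handling, put the subject at risk or interfere with interpretation of data. Lactation is not a disorder.
- Exclusion 7 covers "Any chronic or clinically significant medical condition that, in the opinion of the investigator, would jeopardize the safety or rights of the subject". Lactation is not a medical condition of that kind, and the infant is not the subject.
- Section 8.2.3 asks for a negative pregnancy test. She has one.

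She must still meet every remaining criterion, but none of them turns on lactation.

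**3. How long would she carry drug?** The protocol states no human half-life, so there is no figure to reproduce. The human projection in protocol Table 1 for BGB-DXP604 gives CL = 0.0090 L/h, Vc = 3.79 L, Q = 0.031 L/h and Vp = 1.92 L. For a two-compartment model:

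- k10 = CL/Vc = 0.0090/3.79 = 0.00237 per h
- k12 = Q/Vc = 0.031/3.79 = 0.00818 per h
- k21 = Q/Vp = 0.031/1.92 = 0.01615 per h
- s = k10 + k12 + k21 = 0.02670 per h
- beta = (s − √(s² − 4·k10·k21))/2 = 0.00152 per h
- half-life = ln 2/beta = 455 h = 19.0 days

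The share of the terminal-phase level remaining t days after the dose is 0.5^(t/19.0):

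| Time | Days after dose | Half-lives | Remaining |
|---|---|---|---|
| Day 29 | 28 | 1.5 | about 36% |
| Day 113 | 112 | 5.9 | under 2% |
| 4 months (4 × 30.4375 days) | 121.75 | 6.4 | about 1% |

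Discharge is at Day 3 (Section 7.6.1), so the inpatient stay covers little of this period. The documents give no PK parameters for BGB-DXP593.

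**4. How much drug, and how many subjects?** Inclusion 3 sets a minimum weight of 50 kg. At the planned 30 mg/kg she would receive 50 × 30 = 1500 mg in Cohort 1B. In Cohort 2A, at the maximum allowed doses, she would receive 2 × 1500 = 3000 mg of antibody in total. Protocol Table 3 plans 3 × 6 = 18 active and 3 × 2 = 6 saline subjects. The cap of 30 leaves 30 − 24 = 6 places for replacements. The documents give no figure for how many nursing women might volunteer.

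**The case against.** The strongest objection is that harm to an infant rests on facts outside the documents. Exposure needs antibody to pass into milk and then be taken up by the infant. The documents quantify neither, and the range cannot be narrowed from nil. This stands. A reader might infer that infants will be exposed or harmed, and the documents do not support that. They also report no treatment-related findings in monkeys up to 300 mg/kg and no specific binding to human tissue (Section 1.2.1.2), and they judge a pharmacodynamic effect in healthy subjects unlikely (Section 1.5). None of this is infant data, but it tempers the concern.

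Three further readings go too far:

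- **Both antibodies are first-in-human.** Only BGB-DXP604 is. Section 1.4.2.2 says that BGB-DXP593 has already been given to healthy subjects at 30 mg/kg.
- **Footnote e alone makes a woman eligible.** It does not, because Section 7.2.1 requires all criteria to be met. The point is only that none of them concerns lactation.
- **Pregnancy is unguarded.** It is absent from the numbered exclusions, but the test rule in Section 8.2.3 blocks dosing. Where the rule sits is a matter of drafting.

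The consent form and Investigator's Brochures are not available here and may advise on breastfeeding. That could soften the practical risk. It would not close the gap, because under Section 7.2.1 those documents are not eligibility criteria.

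**Conclusion.** The omission is confirmed. Followed as written, the plan could enrol and dose a nursing woman, and it would not record that she was nursing. The number affected is likely to be small: only the 18 planned active-arm subjects, plus any replacements who receive active drug, could carry it, and not all of them will be women. No infant dose can be calculated. The conclusion rests on the criteria as listed and on the half-life of about 19 days, which is itself a projection from monkeys. It does not depend on any particular amount passing into milk. No endpoint, dose, sample size or analysis is affected. The change is still worth making, because it alters who can be dosed, concerns a third party who cannot consent, and costs little.

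**What to change.** - Add to Section 4.2 an exclusion for women who are breastfeeding at screening or admission. Section 7.3 already repeats the criteria review on Day -1, so no new visit is needed.
- Add lactation status to the reproductive status recorded under Section 8.1.1, and align Appendix 1 footnote e with the new criterion.
- The sponsor should decide whether any breastfeeding restriction applies after dosing, state it, and reconcile it with the contraception period in Inclusion 6. This review does not propose a duration.
- If pregnancy is also listed in Section 4.2, refer to the existing rule in Section 8.2.3: a urine test with serum confirmation, up to dosing on Day 1. An exclusion tied to any positive test at screening or Day -1 would conflict with the serum confirmation and would miss a positive result on Day 1.

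The cost is a protocol amendment, with the regulatory and ethics approval that Section 14.2.1 requires, and one extra screening question. The loss of eligible volunteers should be negligible.
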